The University of Washington is the sponsor of the study which is supported by an anonymous funder who does not have any ownership over the management and conduct of the study, the data, or the rights to publish.

III. Objectives

The objective of the study is to measure the proportion of individuals who are initiated on antiviral therapy within 48 hours of symptom onset using a home-based self-test, followed by a telehealth consultation to diagnose influenza and home delivery of antivirals

Primary Outcome Measures

The primary outcome measure will be the proportion of eligible individuals who initiate antiviral therapy at home within 48 hours of symptom onset utilizing a home-based test and the telehealth app for influenza diagnosis and rapid home-delivery of antivirals. It will be calculated using binomial regression with log link, where the number of drug eligible influenza-diagnosed individuals, defined as the number of individuals eligible to receive BXM with both self-test positive influenza and laboratory-confirmed influenza, reporting administration of the study drug within 48 hours of symptom onset is divided by the total number of drug eligible individuals with both self-test positive influenza and laboratory-confirmed influenza.

Secondary endpoints:

- Proportion of individuals who test positive for influenza using the home-based test within 48 hours of symptom onset
- Proportion of individuals with a positive home-based influenza self-test who have a positive test confirmed by the central laboratory
- Sensitivity and specificity of a self-test compared to a laboratory-based molecular influenza test
- Proportion of individuals who are delivered antivirals within 48 hours of symptom onset
- Proportion of individuals who self-report administration antiviral therapy within 48 hours of symptom onset
- Symptom duration and severity among drug eligible and drug ineligible influenza-positive individuals
- Proportion of families with influenza infection diagnosed within 7 days of an index case (another influenza-positive household member)
- Viral quantity and duration of viral RNA detection among drug eligible and drug ineligible influenza-positive participants
- Proportion of drug ineligible study participants seeking medical care for respiratory illness symptoms
- Proportion of individuals who choose to take a self-test among those who are eligible to take a self-test

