5. Following the prescription, the study pharmacist will dispense and package the BXM. Additionally, an informational hand out regarding the BXM dosing instructions will be included in this package. Furthermore, the individual will receive a post-visit Care Plan through the tele-health app, which will include reminders about the next steps for the study.
6. Following packaging of the study drug, a rapid delivery service will be notified that the intervention is available for delivery.

7. Next, rapid delivery service will pick up the study drug and deliver it in-person to the household of the case.
8. After delivery, the case will take the study drug and record the time of ingestion in the illness questionnaire in REDCap.

Follow-up

Following drug receipt, individuals will be screened 48 hours later to determine whether there is evidence of short-term reaction to the drug. Any short-term evidence reaction to the drug will be treated promptly by consultation with a member of the study medical expert team. In addition, the household will receive the contact information for a medical professional for follow-up questions after initiation of the intervention. Furthermore, the drug eligible participant will also be able to direct drug related questions to a tele-health provider via the tele-health app.

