- 20 mg white to light yellow, oblong shaped film-coated tablets debossed with “Ø772” on one side and “20” on the other side available as:
 - 2 x 20 mg tablets per blister card in secondary packaging: NDC 50242-828-02
 - 4 x 20 mg tablets per blister card in secondary packaging: NDC 50242-828-02
- 40 mg white to light yellow, oblong shaped film-cated tablets debossed with “BXM40” on one side available as:
 - 1 x 40 mg tablet per blister card in secondary package: NDC 50242-860-01
 - 2 x 40 mg tablets per blister card in secondary packaging: NDC 50242-860-02

Upon receiving a prescription for antiviral medication from a tele-health provider, a study pharmacist will pull the blister pack or packs from the correct weight bin, which will be organized prior to the start of the influenza season, and dispense the medication.

Following the packaging and labeling of the intervention, an informational hand out about the study drug will be included in this packaging along with the contact information for a licensed medical professional associated with the study who is available to answer any follow-up questions the participant may have regarding the intervention. Furthermore, the drug eligible participant will also be able to direct drug related questions to a 98point provider via the tele-health app.

Medication delivery and counseling

After the intervention is dispensed, the rapid delivery service will be notified that the study drug is available for delivery. Next, the rapid delivery service will pick up the intervention and deliver the package to the household of the case within 2-6 hours of an influenza diagnosis . Once the medication leaves the storage facility, delivery tracking will be performed by a member of the study staff and a log recording successful medication delivery will be kept as additional quality assurance measure.

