Secondary aim: Determine the social and technical infrastructure that would be required to rapidly detect and interrupt influenza transmission at the household level and to determine whether a home-based self-test and antiviral delivery strategy would be feasible in the context of a pandemic.

Primary Objectives:

P1) To measure the proportion of individuals who are initiated on antiviral therapy within 48 hours of symptom onset using home-based self-test to diagnose influenza and home delivery of antivirals.

Secondary Objectives:

S1) Proportion of individuals who test positive for influenza using the home-based test within 48 hours of symptom onset

S2) Proportion of individuals who are delivered antivirals within 48 hours of symptom onset

S3) Symptom duration and severity among cases and household contacts

S4) Viral titer and duration of viral RNA detection among influenza-positive cases

S5) Cost effectiveness, assessed using health resource utilization and school and work absenteeism

S6) Emergence of antiviral resistance, assessed by genetic sequencing of influenza strains

B. Final Analysis Plan

This section describes the main statistical analyses that will be conducted on enrolled households at DSMB meetings and at the end of the study.

B1. Analysis Datasets

The Primary Dataset will consist of all individuals from enrolled households who enroll in the study, comprised of symptomatic (drug-eligible) individuals.

All eligible and enrolled households will be included in the study unless they meet one or more of the following exclusion criteria:

1. Previous documentation of an influenza infection prior to or during the annual influenza season in any household member prior to enrollment

At the participant level, enrolled individuals meeting any of the following criteria will be excluded from analysis (note: their household may still be eligible, as another eligible member of their household may still enroll):

1. The individual's informed consent is determined to be not valid
2. The individual has been double enrolled in the study. In this case, the individual's data will be used once.
3. No symptom questionnaire is collected.

B2. Variable definitions

[See Tables 1a-c for details]

B3. Baseline Tables and Study Conduct

Description of the main tables and statistical analyses

This section describes the main tables and statistical analyses. Metrics will be updated monthly and presented to the DSMB at each meeting.

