Success = Participant initiated on antiviral therapy within 48 hours of symptom onset
Failure = Participant is not initiated on antiviral therapy (**more than 48 hours** after symptom onset *or* participant **never** initiates antiviral therapy)

Table 1. Estimated secondary attack rates for planned 2019-2020 study aim on household transmission dynamics.

The study is being conducted in the Seattle, WA area over one influenza season. The goal is to enroll at least 250 (up to 1,000) households. Of these, 25% are estimated to have an individual in the household diagnosed with influenza based on estimates from previous household studies.^{23, 28-29}

A table for influenza attack rates by household size is provided below.

Household attack rate	Total households enrolled	Primary cases	Secondary cases (mean household size 5)	Secondary cases (mean household size 4)	Secondary cases (mean household size 3)
25%	250	63	45-96	34-72	23-48

20%	250	50	36-76	27-57	18-38
10%	250	25	18-38	14-29	9-19
Mean household size includes case.					
Secondary attack rate 18-38%, secondary cases presented as a range based on these high and low bounds.³⁰⁻³²					

Incidence Density

Using time-specific variables such as date of enrollment, weekly symptom diaries and questionnaires, Incidence Density (ID) will be calculated, defined with the following formula:

Incidence Density =

Number of participants that successfully initiate antiviral therapy within 48 hours of symptom onset (among participants who have a cough and self-test positive for influenza)

Total person-days

Model

The proportion of individuals that 1) test positive and 2) receive and initiate treatment within 48 hours of symptom onset using home-based self-test and delivery methods will be analyzed with a binomial regression GLMM with a log link. The outcome follows a binomial distribution, with the number of successes in a series of n independent Bernoulli trials, where each trial has probability of success p . Successes here are defined as an individual successfully initiated on antiviral therapy within 48 hours of symptom onset using home-based self-test to diagnose influenza and home delivery of antivirals. The model is defined below:

Incidence proportions of influenza will be presented in tables.

A formal statistical comparisons between study periods (control vs. intervention) will be performed using a Wald test of the hypothesis

$H_0: RR=1$

$H_a: RR \neq 1$

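### SAP B1 excludes anyone with no symptom questionnaire, which conflicts with the protocol's primary denominator and may bias the primary proportion upward

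*SAP*

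**What the plan says.** SAP B1 (Analysis Datasets) lists participant-level criteria under which "enrolled individuals meeting any of the following criteria will be excluded from analysis". The third is "No symptom questionnaire is collected". The SAP does not say which form this means. The study has a weekly symptom log and an illness questionnaire at day 0 and day 7.

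SAP B6, under Outcome, defines "Failure = Participant is not initiated on antiviral therapy". Its parenthesis covers both starting after 48 hours and never starting.

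Protocol III (Primary Outcome Measures) takes as numerator those "reporting administration of the study drug within 48 hours of symptom onset". That count "is divided by the total number of drug eligible individuals with both self-test positive influenza and laboratory-confirmed influenza". Completing a questionnaire is not a condition of the denominator.

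On data sources, Protocol V (Onset of Symptoms, last step for drug-eligible participants) says "the case will take the study drug and record the time of ingestion in the illness questionnaire in REDCap". The Baloxavir paragraph under Medication management also allows ingestion time to be sent through the REDCap app or by text message. Under Medication delivery and counseling, "a log recording successful medication delivery will be kept as additional quality assurance measure".

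Protocol II (Study design) says that once one participant has received baloxavir, nobody else in that household can receive it in the study.

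**The concern.** The study asks whether people get from symptoms to a first dose within 48 hours when the steps are done at home. Recording the dose is the last of those steps, and the illness questionnaire is one place where it is recorded. A rule that keeps only people with a questionnaire may select on how far they got.

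The two documents also treat the same person differently. A confirmed case who returns no questionnaire is a non-success in the protocol's proportion and is absent from the SAP's dataset. The same data can therefore give two primary results, and the SAP version will be the higher one whenever those dropped succeed less often than those kept. Neither document gives a missing-data rule, and the SAP's sensitivity analyses (uniformity of effects, and subsets by time to treatment) do not address this exclusion.

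**Working it through.** **The plan's own figure.** Protocol XI expects 250 × 0.25 = 62.5, rounded to 63 confirmed cases, and a 95% half-width of 0.12 or less. The worst-case half-width is 1.96 × 0.5/√63 = 0.123, so the figure reproduces.

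**Inputs for the illustration.** n = 63 is taken from the protocol as the size of the primary denominator. The share with no questionnaire (m) is not in the documents and is assumed to be 5% to 20%. The success proportion among those kept (p) is not given either, since the plan says only that it should be large. It is assumed to be 0.60 to 0.90.

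**Formulas.** With k dropped and s successes among those kept, the exclusion reports s/(63 − k). If every dropped case is a failure, the full-denominator value is s/63. If every dropped case is a success, it is (s + k)/63. In proportions, the exclusion overstates by p × m in the first case and understates by (1 − p) × m in the second.

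**Results with p about 0.80.**

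| Dropped | After exclusion | All dropped fail | All dropped succeed |
|---|---|---|---|
| 3 (5%) | 48/60 = 0.800 | 48/63 = 0.762 | 51/63 = 0.810 |
| 6 (10%) | 46/57 = 0.807 | 46/63 = 0.730 | 52/63 = 0.825 |
| 9 (15%) | 43/54 = 0.796 | 43/63 = 0.683 | 52/63 = 0.825 |
| 13 (20%) | 40/50 = 0.800 | 40/63 = 0.635 | 53/63 = 0.841 |

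Over the whole assumed range (p from 0.60 to 0.90, m from 5% to 20%), the exclusion overstates by about 0.03 to 0.19 if all dropped cases fail. It understates by about 0.01 to 0.08 if all succeed.

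**Against the planned precision.** If all dropped cases fail, the bias reaches the design half-width when m = 0.123/p. That is about 14% missing at p = 0.90, 15% at 0.80, 18% at 0.70 and 21% at 0.60. Precision itself changes little: the worst-case half-width goes from 0.123 to 0.127 with 60 cases and 0.139 with 50.

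**Which denominator this covers.** The arithmetic uses the protocol's denominator. The cumulative-incidence formula in SAP B6 instead divides by influenza-free participants at baseline, and these figures do not apply to it.

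**The case against.** The strongest reply is that the exclusion may touch few people. If a weekly log counts as a symptom questionnaire, almost everyone has one. If the illness questionnaire is meant, its day 0 part comes before prescribing and delivery in the protocol's sequence, so someone who completes it and stops later is not excluded. Someone who stops right after the self-test and mails no swab has no laboratory confirmation and is outside the protocol's denominator anyway. The people at issue are those who mailed a swab but returned no questionnaire. All of this stands. It limits the likely size, but it does not remove the conflict between the documents or the need to define the form.

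A second reply is that the direction is not proven, and this also stands. That people who return no form start drug less often is a reasonable inference, but the documents do not say so, and the bias reverses if they mostly took it.

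A reader might also infer that the delivery log can score most of the excluded people. The documents do not support that. The log is described only as recording successful delivery, and no split between delivered and undelivered cases is given. It can identify people to whom nothing was delivered. For the others, a delivery time is only a lower bound on ingestion time, and symptom onset is not described as part of the log. The telehealth step is described as a check that symptoms have lasted under 48 hours, not as a source of a recorded onset time.

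**Conclusion.** The point holds as an inconsistency with a plausible upward bias. Criterion 3 contradicts the protocol's primary denominator and sits badly with the SAP's own failure definition. It also makes entry to the analysis depend on a form that can carry the outcome.

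The size is unknown. At 10% dropped and about 80% success among those kept, the reported 0.81 stands against a possible range of 0.73 to 0.83. The larger risk is upward, because the downward risk is limited to (1 − p) × m.

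A reader might treat 0.90 × (1 − m), which gives 0.855, 0.81 and 0.72 at 5%, 10% and 20% missing, as the true proportions behind an observed 0.90. These are only the lower bounds. They assume that every dropped case failed, and neither the 0.90 nor the missing rates come from the documents.

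**What to change.** - Do not apply criterion 3 to the primary endpoint. State which form the term symptom questionnaire means wherever the criterion is kept for other analyses.
- Use the denominator in Protocol III: all drug-eligible, self-test-positive, laboratory-confirmed individuals.
- Count as non-successes the cases with no drug delivered, and the cases with no reported administration from any source (questionnaire, REDCap app or text message). This follows the protocol's numerator and the SAP's failure definition.
- State how later cases in a household that can no longer receive delivery enter the denominator, and reconcile this with Protocol III. Without that, scoring no delivery as a failure would count people whom the protocol itself bars from delivery.
- For delivered cases with no ingestion time, report best-case and worst-case bounds, using delivery and onset times where records allow. Delivery more than 48 hours after a known onset is a failure in both bounds. Otherwise the case is a success in one bound and a non-success in the other.

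The cost is SAP wording and linkage of records, mostly ones already planned. The reported proportion may be lower, and a few delivered cases that did take the drug on time may be scored as non-successes in the main analysis. The bounds show how much that could matter. The change does not recover people who return no swab, since they remain outside the laboratory-confirmed denominator.
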